A subset of approximately 60 subjects enrolled and vaccinated in the first year of the study at Duke will be included in a repeat vaccination sub-study in the second year of the study. The sub-study will explore the safety and immunogenicity of repeat vaccination with the same vaccine product in the subsequent influenza season. The study enrollment procedures will be the same, with the following modifications: At the time of enrollment in the first year, the subjects will be asked in sequential order if they would like to participate in a repeat vaccination sub-study during the next season. The first subjects enrolled at Duke (up to n=60), who express interest in this repeat vaccination sub-study will be included. Subjects need not consent to this part of the study to participate in the main study. In the first year, this convenience sample of sub-study subjects will undergo the same randomization procedures as other subjects in section 5.2.1. The subjects will complete procedures for the first study influenza season as in section 5.1. Contact information will be maintained, and subjects will be contacted and reminded to return to the study center in September/October the next influenza season. Upon return for the second year of the study, subjects will be consented for the sub-study and screened to see if they continue to meet the study eligibility criteria. In year 2, these subjects will receive the same vaccine product as in year 1, using the formulation licensed by FDA for the year 2 season; influenza strains included in the vaccines may be different in the consecutive years. These subjects will remain blinded to the vaccine product in Year 2. Year 1 study participants will only be enrolled in Year 2 of the study if they consent to and are still eligible for participating in the sub-study on repeat vaccination.

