6 LABORATORY ANALYSES

6.1 Influenza Hemagglutination Inhibition (HAI) Assay

Influenza Hemagglutination Inhibition (HAI) Assays will be performed on sera collected, contingent on additional funding. Briefly, reference wild-type, reassortant, or vaccine virus strains representative of the specific viral antigens included in the 2017-2018 and 2018-2019 influenza vaccine will be used to evaluate the relative levels of all three influenza strain-specific antibodies in participant serum samples collected pre- and 28 days post-vaccination from all study participants and at 181 days post-vaccination in a subset of 100 participants at Duke. To accomplish these activities all participant samples will be interrogated for influenza antibodies against the strains of interest using the influenza hemagglutination inhibition assay (HI). This assay is considered the “gold-standard” measure by which to evaluate seroconversion/seroprotection in response to seasonal influenza vaccination. This assay will be performed in accordance with the Duke Regional Biocontainment Laboratory Virology Unit's fully optimized and approved SOP (RVUSOP004 Influenza HI of Serum Samples). Briefly, test samples will be assayed by HAI as duplicate 2-fold dilution series starting at 1:10. Serum dilutions are then incubated with a concentration of virus verified to possess a known potential for red blood cell (RBC) agglutination. The presence of virus-specific antibodies is visualized via incubation of the virus-serum mixture with a RBC solution; the endpoint titer for a given dilution series is then expressed as the reciprocal of the final dilution in which complete HAI is observed. By convention, seronegative samples are defined as having an endpoint HAI titer < 40 and seropositive samples as having an endpoint titer of $\geq 1:40$; and seroconversion as a 4-fold change in endpoint titer relative to pre-immunization baseline or a change from <10 to $\geq 1:40$ ³⁷.

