7.1.1 Sample Size

Safety: Based on data from prelicensure studies^{4,5,7}, we assume that 5% of older adults have moderate/severe injection-site reactions after aIIV3 or IIV3-HD. We have selected a clinically meaningful non-inferiority margin of 5%. Statistical calculations, without consideration of drop-out, show that with an alpha of 0.025 (one-sided), we would need 668 total subjects (334 subjects in each group across all study sites) to have at least 80% power be able to demonstrate that the proportion of moderate/severe pain was non-inferior after aIIV3 vs. IIV3-HD. Enrollment in this study shall occur during two influenza seasons (2017-18 and 2018-19).

Immunogenicity: Based on data from prelicensure studies^{4,5,7}, we conservatively estimate that 50% of older adults demonstrate seroconversion after vaccination with aIIV3 or IIV3-HD for the H3N2 strain. We have selected a clinically meaningful non-inferiority margin of 10%. Statistical calculations, without consider of drop-out, show that with an alpha of 0.025 (one-sided), we would need 780 total subjects (390 subjects in each group across all study sites) to have approximately 80% power to able to demonstrate that the seroconversion rate after aIIV3 was non-inferior to IIV3-HD.

The total number of subjects needed for this study was derived based on 4 factors: 1) Sample size needed for adequate statistical power to test the safety hypothesis; 2) sample size needed for adequate statistical power to test the immunogenicity hypothesis; 3) potential for subject drop-out; and 4) feasibility of dividing subjects across 2 sites. Based on these considerations, the study aims to enroll at least 880 subjects to assess both the safety and immunogenicity endpoints. The study aims to enroll at least 720 to test only the safety hypothesis.

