The proportion and 95% exact binomial confidence interval of serious adverse events and events of clinical interest, as well as the total number of events, will be presented by site, vaccine group, severity, and relatedness. Listings of the serious adverse events will also be presented. This information will also be prepared for the subset ($N \geq 176$) of subjects 80 or older.

7.1.5 Primary Objective 3

- To compare the seroconversion rate for the H3N2 influenza A strain after aIIV3 and IIV3-HD in the full study population
 - Hypothesis: the seroconversion rate for the H3N2 influenza A strain in the full study population after aIIV3 will be non-inferior to IIV3-HD

This objective will be assessed using a one-sided non-inferiority test with the alpha level set at 0.025 and non-inferiority margin of 10%.

The null hypothesis is the allV3 H3N2 seroconversion rate is inferior to IIV3-HD seroconversion rate.

$$H_0: \text{allV3 H3N2 rate} - \text{IIV3-HD H3N2 rate} \geq 0.1 \text{ (10\%)}$$

The alternative hypothesis is the allV3 H3N2 seroconversion rate is non-inferior to IIV3-HD H3N2 seroconversion rate.

$$H_a: \text{allV3 H3N2 rate} - \text{IIV3-HD H3N2 rate} < 0.1 \text{ (10\%)}$$

The upper bound of the one-sided binomial confidence interval of the difference will be used to make this assessment.

7.1.6 Secondary Objective 1

- To compare the proportions of local and systemic reactions after allV3 and IIV3-HD in the full study population and by age-group (65-79 years and ≥ 80 years) (other than moderate/severe injection site pain in the full study population)

The proportions in the full study population will be conducted as for Primary Objective 1 using a non-inferiority test to determine if allV3 is non-inferior to IIV3-HD with a 5% non-inferiority margin. These secondary objectives will be conducted with a one-sided alpha at the 0.01 level to adjust for multiple comparisons. It is recognized that with 12 different assessments at the alpha 0.01 level (given the events are truly independent) we are allowing an 11.4% chance of making a type I error.

The age-group assessments will be assessed using standard two-sided 95% confidence boundaries of the difference in proportions between the groups. No formal statistical testing will be implemented for the age-group comparisons.

7.1.7 Secondary Objective 2

- To describe and compare changes in health-related quality of life after allV3 and IIV3-HD in the full study population and by age-group

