To compare serum hemagglutination inhibition (HAI) antibody titers after aIIV3 and IIV3-HD for each of the three influenza vaccine strains contained in the respective vaccine for that season in the full study population and by age-group (except for seroconversion for the H3N2 strain in the full study population)

Responses to each influenza antigen will be analyzed, with the exception of seroconversion for H3N2, which is analyzed in Primary Objective 1. The proportion of subjects with seroprotection (pre- and post-immunization) seroconversion (4-fold rise from baseline) in the two treatment groups will be presented along with 95% exact binomial confidence intervals. A 95% confidence interval of the difference in proportions between the treatment groups will also be presented.

The GMTs for each influenza antigen, including H3N2, and 95% confidence boundaries will be presented for both treatment groups. A 95% confidence interval of the difference in GMTs between the treatment groups will also be presented. This information will also be prepared for the subset (N≥176) of subjects 80 or older.

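### The H3N2 seroconversion test takes no account of season, and no season-specific HAI result is written into the plan, although vaccine strains may change between the two seasons

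*Combined protocol and SAP*

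**What the plan says.** Primary Objective 3 (section 7.1.5) has one hypothesis, that "the seroconversion rate for the H3N2 influenza A strain in the full study population after aIIV3 will be non-inferior to IIV3-HD". The test is stated as: "This objective will be assessed using a one-sided non-inferiority test with the alpha level set at 0.025 and non-inferiority margin of 10" percent. Section 7.1.1 gives no season-specific rate: "we conservatively estimate that 50% of older adults demonstrate seroconversion after vaccination with aIIV3 or IIV3-HD for the H3N2 strain", and "we would need 780 total subjects (390 subjects in each group across all study sites) to have approximately 80% power". To allow for drop-out, "the study aims to enroll at least 880 subjects to assess both the safety and immunogenicity endpoints".

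Section 4.3 plans about 220 subjects per season at Duke, about 170 per season at Boston, and about 100 at Cincinnati in 2018-19 only. It notes, for the repeat-vaccination sub-study, that "influenza strains included in the vaccines may be different in the consecutive years". Section 6.1 has sera tested with "strains representative of the specific viral antigens included in the 2017-2018 and 2018-2019 influenza vaccine".

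For the secondary HAI outcomes, section 7.1.8 says "Responses to each influenza antigen will be analyzed, with the exception of seroconversion for H3N2". It calls for proportions, GMTs and between-arm intervals. The objective refers to the strains in that season's vaccine, but the only breakdown written is age. The one sensitivity analysis (section 7.1.9) concerns injection-site pain. The randomization strata in section 5.2.1 are site and age group.

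**The concern.** Season can decide which virus is being measured. If the H3N2 component changes between years, a Year 1 subject and a Year 2 subject contribute responses to different antigens, and the relative performance of the two vaccines may differ too. Site mix also shifts, because Cincinnati enrolls only in Year 2.

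Two things are at stake. The first is precision: differences between seasons in the overall response are left in the standard error when they could be removed. The second is interpretation: a pooled finding of non-inferiority could rest on one favorable season offsetting an unfavorable one, and nothing specified in sections 7.1.5, 7.1.8 or 7.1.9 would bring that to light. For section 7.1.8 there is also ambiguity. Two analysts could produce different tables from the same text.

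**Working it through.** All power figures use the normal approximation and the intended direction of the test (aIIV3 minus IIV3-HD above -10 points). The hypotheses printed in 7.1.5 place the margin at +0.1; that is a separate matter.

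**1. The plan's own figure.** At 50% in both arms, n per arm = (1.96 + 0.8416)² × (0.25 + 0.25) / 0.10² ≈ 393, or 786 in total, against the stated 390 and 780. At 390 per arm, SE = √(0.5/390) = 0.0358 and power = Φ(0.10/0.0358 − 1.96) = 79.8%. The stated figure reproduces.

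**2. Season sizes (section 4.3).** Year 1: 220 + 170 = 390. Year 2: 220 + 170 + 100 = 490. Weights: w₁ = 390/880 = 0.443 and w₂ = 490/880 = 0.557.

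**3. Precision, seroconversion.** Assume rates of 30% in Year 1 and 60% in Year 2, no difference between arms, 390 evaluable per arm, and arms balanced within season.
- Pooled rate: 0.443 × 0.30 + 0.557 × 0.60 = 0.467. Pooled variance: 0.467 × 0.533 = 0.2489. SE = √(2 × 0.2489/390) = 0.0357.
- Within-season variance: 0.443 × 0.21 + 0.557 × 0.24 = 0.2267. SE = √(2 × 0.2267/390) = 0.0341.
- Crude power: the interval uses 0.0357 but the estimate varies with 0.0341, so Φ((0.10 − 1.96 × 0.0357)/0.0341) = Φ(0.879) = 81.0%.
- Stratified power: Φ(0.10/0.0341 − 1.96) = Φ(0.973) = 83.5%.

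At 40% and 60% the figures are 80.2% and 81.3%. At 50% in both seasons they are both 79.8%.

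**4. Precision, GMTs (if pooled).** CI width is multiplied by √(1 + w₁w₂ × shift²/SD²), with w₁w₂ = 0.247. The shift and SD are assumptions, in log2 units.

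| Season shift | SD 1.5 | SD 2.0 |
|---|---|---|
| 1 (2-fold) | 1.05 | 1.03 |
| 2 (4-fold) | 1.20 | 1.12 |

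The interval is therefore about 3% to 20% wider.

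**5. Masking.** Assume a 50% rate for IIV3-HD in both seasons and 390 evaluable per arm. P(declare) ≈ Φ((0.10 + d)/0.0358 − 1.96), where d = w₁d₁ + w₂d₂.

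| True difference Year 1 / Year 2 (points) | Pooled d | P(declare non-inferiority) |
|---|---|---|
| +5 / -12 | -4.5 | 34% |
| -12 / +5 | -2.5 | 55% |
| -12 / 0 | -5.3 | 26% |

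**6. What season-specific results would look like.** Half-width = 1.96 × √(0.5/n per arm).
- All 880 evaluable: 9.9 points in Year 1 (195 per arm) and 8.9 in Year 2 (245 per arm).
- 780 evaluable in the same ratio: 10.5 and 9.4 points, against 7.0 pooled.
- Power for the 10-point margin within one season: 50.6% and 60.0% with all 880, or 46.0% and 54.9% with 780.

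**The case against.** The strongest reply is that the pooled comparison is sound as it stands. Seroconversion is a within-subject response to the vaccine received, so its proportion over two seasons is a coherent average. Arms are randomized 1:1 concurrently in permuted blocks by site, so season is approximately balanced between them. This stands: a reader might infer that pooling biases the result, and the documents do not support that.

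A reader might also infer that season differences take power below the planned level. They cannot. Sizing at 50% already uses the maximum binomial variance of 0.25, and step 3 shows crude power at or above 79.8%. What is lost is an available gain.

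Nor do the documents establish that every HAI outcome is pooled. Section 2.2.2 and the objective in 7.1.8 refer to the respective season's vaccine, and reporting by season is a fair reading. Section 7 describes itself as a summary of a fuller SAP still to be developed, so season tables may appear there. This narrows the point on 7.1.8 to an ambiguity. It does not remove the point on 7.1.5, where the analysis is stated in full and without season.

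Lastly, masking needs offsetting seasons, for which the documents give no evidence. In the +5 and -12 case the pooled test still fails about 66% of the time, and with a pooled truth of -4.5 points a declaration is correct for the full-population hypothesis as written. That is accepted. The gap is that a reader of the results could not see the pattern.

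**Conclusion.** The point holds as one of precision, reporting and clarity. Section 7.1.5 specifies a single comparison without season, and 7.1.8 leaves the handling of season open. The cost in precision is modest for seroconversion (about 2.5 points of power at assumed rates of 30% and 60%, and none if the rates are equal). It could be larger for pooled GMTs (CI 3% to 20% wider under the assumed shifts and SDs). The chance of declaring non-inferiority while one season lies beyond the margin ranges from about 26% to 55% in the three cases worked. Those season differences are illustrative assumptions.

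A reader might go on to require non-inferiority in each season, or to limit the pooled claim when one season's estimate passes the margin. The design does not support that: single-season power is only about 46% to 60%, and either rule would add a second success condition to a hypothesis stated for the full population.

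**What to change.** - **Section 7.1.5:** estimate the H3N2 seroconversion difference stratified by season, with Mantel-Haenszel weights or a stratified Miettinen-Nurminen interval.
- **Section 7.1.8:** do the same for the other seroconversion and seroprotection differences, include season in the log-titre model, and state explicitly which results are pooled and which are by season.
- **Reporting:** for each strain, show Year 1 and Year 2 differences or GMT ratios with 95% CIs beside any pooled figure. Label them descriptive, with no requirement of non-inferiority in each season.

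The cost is SAP wording and one extra table, with no new data and no loss of power for the primary test. The season-specific intervals will be wider than the pooled one, by the amounts in step 6, and should be read with that in mind.

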2.2 Study Outcome Measures

Where possible, all outcome measures will be evaluated and compared between the two treatment groups for the full population and in both age subsets (65-79 years and ≥ 80 years)

2.2.1 Primary Outcome Measures:

1. Comparison of the proportion of subjects reporting moderate/severe injection site pain within the first week post-vaccination in both treatment groups.
2. The frequency and descriptions of serious adverse events and adverse events of clinical interest observed in the two treatment groups.

3. H3N2 HAI seroconversion: The proportion of subjects achieving H3N2 seroconversion at day 29 (an HAI titer \geq 1:40 at day 29 if the baseline titer is $<$ 1:10 or a minimum four-fold rise in HAI titer if the baseline titer is \geq 1:10) in the respective season's vaccine.

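### Primary Objective 3 tests H3N2 seroconversion in the wrong direction: as written, a clearly less immunogenic aIIV3 is declared non-inferior and a clearly more immunogenic one is not.

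*Combined protocol and SAP*

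**What the plan says.** In words, section 7.1.5 is clear. The hypothesis is that "the seroconversion rate for the H3N2 influenza A strain in the full study population after aIIV3 will be non-inferior to IIV3-HD", and the null is put as "The null hypothesis is the allV3 H3N2 seroconversion rate is inferior to IIV3-HD seroconversion rate". The test is one-sided at alpha 0.025 with a margin of 10%. Section 2.2.1 defines the endpoint as "The proportion of subjects achieving H3N2 seroconversion at day 29", meaning a titer of at least 1:40 from a baseline below 1:10, or at least a four-fold rise otherwise. A higher proportion is therefore better.

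The formulas in the same section are:

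- H0: aIIV3 rate − IIV3-HD rate ≥ 0.1
- Ha: aIIV3 rate − IIV3-HD rate < 0.1

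The decision rule follows: "The upper bound of the one-sided binomial confidence interval of the difference will be used to make this assessment". The same sentence closes section 7.1.3, which tests moderate/severe injection-site pain with H0: aIIV3 − IIV3-HD ≥ 0.05 and Ha: < 0.05.

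**The concern.** The form in section 7.1.3 suits a harm: a large positive difference means more pain on aIIV3, and the upper bound must stay below the margin. Section 7.1.5 reuses it for a benefit without reversing it. A difference of +0.10 or more then means that aIIV3 seroconverts at least 10 points more often, and the formula labels that outcome inferior. Any deficit, however large, lies inside the alternative.

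This is the formal decision rule for one of the two primary objectives that carry a hypothesis test. A program built from the formulas would report non-inferiority for a vaccine that is materially less immunogenic, and could deny it to one that is more immunogenic. An analyst who noticed and silently reversed the rule would be departing from the prespecified test, and that could be challenged whichever way the result fell.

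**Working it through.** **Inputs.** Section 7.1.1: 50% seroconversion in both arms, margin 10 points, one-sided alpha 0.025, 390 per arm (780 total) before drop-out, about 80% power, enrollment of at least 880. Section 5.2.1: 1:1 allocation, hence 440 per arm at full enrollment.

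**Reproducing the plan's figure.** Unpooled normal approximation, true difference zero:

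n per arm = (1.960 + 0.842)² × (0.5×0.5 + 0.5×0.5) / 0.10² ≈ 392.4, so 393 (786 total), against 390 (780) in the plan.

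Power at 390 per arm: SE = √(0.5/390) = 0.0358; Φ(0.10/0.0358 − 1.960) = 79.8%. The plan's figure is reproduced.

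**The two rules.** Let d be the true difference aIIV3 − IIV3-HD, with IIV3-HD at 0.50 and aIIV3 at p = 0.50 + d. Then SE = √[(0.25 + p(1−p))/n].

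- As written (upper 97.5% bound < +0.10): P(declare) = Φ((0.10 − d)/SE − 1.960)
- Corrected (lower 97.5% bound > −0.10): P(declare) = Φ((0.10 + d)/SE − 1.960)

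Example at d = −0.10: p = 0.40 and SE = √(0.49/390) = 0.0354. As written: Φ(0.20/0.0354 − 1.960) = Φ(3.68) = 0.9999. Corrected: Φ(0 − 1.960) = 0.025.

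Probability of declaring aIIV3 non-inferior, 390 per arm:

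| True difference (points) | As written | Corrected |
|---|---|---|
| −20 | about 1.000 | <0.0001 |
| −10 | 0.9999 | 0.025 |
| −5 | 0.987 | 0.288 |
| 0 | 0.798 | 0.798 |
| +3 | 0.499 | 0.953 |
| +5 | 0.288 | 0.987 |
| +10 | 0.025 | 0.9999 |

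Simulation (200,000 trials, 390 per arm) agrees: at −10 points, 0.9998 as written and 0.023 corrected; at +5 points, 0.281 and 0.987. At 440 per arm the written rule gives about 1.000 at −10, 0.843 at 0, 0.318 at +5 and 0.025 at +10.

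**What single results would look like (390 per arm).** With observed rates of 30% on aIIV3 and 50% on IIV3-HD, the interval for the difference is −26.7 to −13.3 points. It lies wholly beyond the intended margin, yet the upper bound is below +10, so the written rule declares non-inferiority. With 60% against 50%, the interval is +3.1 to +16.9. aIIV3 is better with the lower bound above zero, yet the upper bound exceeds +10, so the written rule does not declare non-inferiority.

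**Where a better aIIV3 starts to fail.** The upper bound reaches +0.10 when the observed difference is about 0.10 − 1.960 × 0.0358 = +3.0 points (+3.4 at 440 per arm).

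**Why the power calculation hides the error.** At d = 0 the two formulas coincide, so both give 79.8%. That is equal probability, not the same verdict in each trial. At d = 0 both rules pass only if the observed difference is within about ±3.0 points, which has probability 2 × 0.7975 − 1 = 59.5%. In the other 40.5% of trials one rule passes and the other fails.

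**The case against.** The strongest reply is that the intent is beyond doubt. The summary, section 2.1.1, section 7.1.1 and the words of section 7.1.5 all describe non-inferiority of aIIV3, so a careful analyst would test it correctly whatever the formulas say. Section 7 also calls itself a summary of a comprehensive statistical analysis plan still to be written. That plan is not in the document reviewed and may already have the rule right. HAI testing depends on funding (sections 3.2.1 and 6.1), and section 7.1.1 allows a safety-only study, so the test might never be run.

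These points limit the certainty of harm and leave the error in place. Both inequalities, the sign of the margin and the named bound all point the same wrong way, so this is not a stray symbol. Nothing in the document reverses the subtraction or uses a lower bound for seroconversion. Because the section contradicts itself, someone must choose between its words and its formulas, and that choice should not be left until data exist.

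One qualification stands: a better aIIV3 fails only once its observed advantage reaches about 3 points at the planned size. At a true advantage of 2 points the written rule still passes about 61% of the time. No such qualification applies to passing a clearly worse aIIV3.

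**Conclusion.** The concern holds and must be fixed before analysis. Applied as written, the type I error at the intended boundary (aIIV3 10 points worse) is about 99.99% instead of 2.5%, and a true 5-point advantage for aIIV3 is called non-inferior only 28.8% of the time.

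The figures assume 50% seroconversion on IIV3-HD, 390 evaluable per arm and a normal-approximation interval, since section 7.1.5 does not name the interval method. The error of direction depends on none of these. The finding covers the text of section 7.1.5 only. Section 7.1.3, Primary Objective 2 and the sample size are unaffected.

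**What to change.** Rewrite section 7.1.5 as:

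- H0: aIIV3 rate − IIV3-HD rate ≤ −0.10
- Ha: aIIV3 rate − IIV3-HD rate > −0.10
- Declare non-inferiority if the lower bound of the one-sided 97.5% confidence interval for aIIV3 − IIV3-HD exceeds −0.10.

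Reversing the subtraction to IIV3-HD − aIIV3 and keeping the upper bound below +0.10 is equivalent; use one form throughout. Leave section 7.1.3 unchanged. Check that the comprehensive statistical analysis plan and its programs follow the corrected rule, and date the change before unblinding.

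The cost is a few lines of text. No further subjects or data are needed, and power at equality remains 79.8% at 390 per arm.
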